Participants will be asked to complete a total of 3 surveys. Surveys will be administered via paper, online through an email link to the survey sent by Rutgers Population Science Datstat Illume Survey Software, or via phone with research staff. The baseline is administered when participants first enter the study, follow-up survey #1 is to be completed at the time of a post-op appointment, usually between 2-4 weeks after surgery and follow-up survey #2 is to be completed 6 months after the baseline survey. For both follow-ups, participants will be sent a link to the survey via email or they may also be contacted by telephone to complete the follow-up surveys. If requested, we can mail a copy of the follow-up survey to participants with a pre-paid envelope to return the survey. For follow-up #1 research staff will provide the participant with the follow-up survey at an appointment. The participant can complete the survey in clinic or they can take it home to return via mail in a pre-paid envelope. For patients who indicated a preference to complete the follow-up survey electronically, research staff will visit the participant at her appointment and remind her that the survey will be sent via email link. If patients take the survey home or prefer electronic surveys, staff will contact participants weekly and, if contact is not made within two weeks, the participant may be considered a survey refuser or drop. If participants skip the first follow-up survey, we will still send them the second follow-up survey at 6 months. We allow participants access to the website for the study duration. We do not anticipate that they will view the B-Sure website simply to look up answers for the follow-ups.

We will track website use to evaluate this possibility. Participants are paid \$25 for each survey they complete for a total of \$75. Rutgers Cancer Institute of New Jersey will provide payments to MSKCC participants in the form of gift cards which will require Rutgers staff to receive contact information (including names, address, email and phone #s) for MSKCC participants. MSKCC study consent will detail that Rutgers CINJ staff will receive their contact information to carry out study procedures. Research recruiters and site investigators [name], [name] and [name] will meet bi-weekly to review study accrual and troubleshoot enrollment challenges.

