3.2.3. Sample Size for RCT. We anticipate we will recruit participants for about 6months (months 17-22). Our goal is to enroll 90 to 130 women (65 in UC and 65 in CPM DA). We are anticipating a 70-75% acceptance rate based on our BRDA study. To obtain $N = 130$ (90 MSKCC, 10 CINJ, 30 MGH), we estimate approaching 169-182 women. Because acceptance rates are a study goal, this is only an estimate, and thus we allow 6-12 months for accrual.

3.2.4 Usual Care. Usual care consists of what traditionally occurs at both sites. At both sites, the surgical oncologist educates WSC regarding the facts about CPM, including the fact that it is not medically indicated, and does not reduce the risk of the spread of cancer. If interested, the patient is referred to a plastic surgeon.

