5.1. Primary Aim: Is the intervention trial feasible?

Approach and Analysis

For feasibility, 2 questions will be addressed: 1) Are patients joining/staying in the trial? We judge this study feasible if the participation rate (consented and complete baseline) is equal to or greater than 70% and the retention rate at follow-up is 85%. These "yardsticks" were selected to ensure there is sufficient interest to proceed to a larger scale trial. 2) Are participants using the DA in the way that was intended? We will evaluate log-ins, pages viewed, and how long modules are viewed. If participants review more than 75% of the pages, we will consider this acceptable usage. To evaluate the acceptability, we will

examine: whether participants use the DA, to what degree they use it, and factors predicting uptake and use. We will also look at whether patients 1) opened the web aid and 2) viewed each page. First, basic descriptive information will be gathered regarding participant log-ins and number and duration of log-ins. Second, DA evaluation and User Interface Satisfaction surveys will be examined.

We will judge the DA as acceptable if 75% of participants used it and if the average score was > 5.6/7 on the DA evaluation. *Using regression analyses, we will examine the following for association with DA use: younger age, internet familiarity, and higher education. The small sample (N = 40) and limited range of correlate categories limits options for statistical analyses. Missing values will be imputed from observed information (SAS Procedures MI and MIANALYZE). Confidence intervals and inferential procedures will adjust for uncertainty due to imputation.*

Table 1. Probability of declaring feasibility under various assumptions

Feasibility Component	Unaccept-able Rate	Acceptable Rate	Decision rule for claiming Feasibility	Prob. Declare Feasible under Unacceptable Rates	Prob. Declare Feasible under Acceptable Rates
Acceptance Rate	65%	70%	If 80 women recruited by the 114th (inclusive) approached	5%	96%
Completion Rate	79%	85%	If 68 participants complete survey	5%	96%

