Power. We expect to approach a maximum of 140 to enroll 100 women. If 100 women are enrolled in the study by the 140th patient approached and 85/100 participants complete the survey, then we will declare the study feasible. We chose the sample size and decision rules so that the probability of declaring feasibility would be approximately 5% under unacceptable rates of acceptance and completion and exceed 95% under acceptable rates. Power calculations are in **Table 1**. If the true acceptance and completion rates are 65% and 79%, respectively, which we consider to be too low to warrant further research, then the probability of declaring feasibility would be 5%. If the true acceptance and completion rates are 70% and 85%, respectively, which we consider large enough to warrant further research, then the probability of declaring feasibility would be 96%. These figures are based on binomial distributions

5.2. Secondary Aim 2: What is the impact of DA on CPM knowledge, psychosocial factors, decisional conflict, completeness of preparation, and CPM intention?

Approach and Analysis. Our outcomes are knowledge, perceived risk for recurrence, cancer worry, coping efficacy, anxiety, decisional conflict, preparedness, and intention. We anticipate that 100 women will complete the baseline and 85 will complete the follow-up. We will characterize the data using standard methods (means, medians, standard deviations, 95% confidence intervals) for the sample and separately by study arm. In exploratory analyses, we will use two sample repeated measures to compare outcomes using an intent-to-treat approach. We will assess associations among the outcome variables using Pearson's correlation coefficients. We will also characterize the patterns of missing data.

6. Reporting Results

The policies and procedures of Rutgers University's legal department (see: Investigator's Handbook) will govern publication of the results of this trial. The results of this trial will be submitted for publication in a timely manner following its conclusion. The Rutgers Cancer

Institute of New Jersey PI and all co-authors will review any abstract of manuscript prior to its submission.

7. Bibliography

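### Enrolment size and acceptance rule are stated in several unreconciled ways, the 5% and 96% hold for neither fixed rule, and the 70% yardstick's false-pass rate depends on when accrual closes

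*Combined protocol and SAP*

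**What the plan says.** **Size.** Section 3.2.3: "Our goal is to enroll 90 to 130 women (65 in UC and 65 in CPM DA"). It splits the 130 by site (90, 10 and 30). To reach 130, "we estimate approaching 169-182 women". Because acceptance is itself an outcome, that number is called an estimate, "thus we allow 6-12 months for accrual". Nothing says where between 90 and 130, or between 6 and 12 months, enrolment closes.

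**Acceptance rule, three forms, all in section 5.1.**
- The yardstick: "participation rate (consented and complete baseline) is equal to or greater than 70% and the retention rate at follow-up is 85" per cent. It gives neither a number approached nor a time of judgement.
- Table 1: "If 80 women recruited by the 114th (inclusive) approached", with 68 completing the survey.
- The Power text: 100 enrolled by the 140th woman approached, and 85 of 100 completing.

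**Claimed performance.** The Power text says: "We chose the sample size and decision rules so that the probability of declaring feasibility would be approximately 5% under unacceptable rates" and above 95% under acceptable ones. The unacceptable rates are 65% acceptance and 79% completion; the acceptable rates are 70% and 85%. Table 1 prints 5% and 96% separately on the acceptance row and the completion row. The Power text attaches the same figures to the two rates together and says they are binomial.

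**Monitoring.** Under section 3.2.2, recruiters and site investigators "will meet bi-weekly to review study accrual and troubleshoot enrollment challenges".

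**The concern.** Acceptance is half of the primary go/no-go decision on a larger trial. A reader cannot tell which rule decides it, and the rules can disagree on the same data. If 98 of the first 140 women enrol, the 70% yardstick is met exactly (98/140 = 70.0%) and the Power-text rule fails. If enrolment closes between 90 and 99, which section 3.2.3 permits, the Power-text rule cannot be met at all.

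Two consequences follow. First, the 5% and 96% have to be checked against each fixed rule, since the plan relies on them to justify the sample size. Secondly, a yardstick without a denominator is applied to whatever sample exists at the end of enrolment. Acceptance is not blinded, and the end of enrolment is left open, so the chance of passing depends on how and when accrual is closed.

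**Working it through.** **Inputs.** Unacceptable and acceptable acceptance rates 65% and 70%; completion rates 79% and 85% (5.1, Power text). Rules: 80/114 and 68 completers, taken as 68/80 from the acceptance row (Table 1); 100/140 and 85/100 (Power text); at least 70%, no denominator (5.1). Enrolment 90 to 130 (3.2.3). Assumption: women accept independently at a constant rate.

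**Step 1: the plan's own figures.** For a rule of at least r of n, the pass probability is P(X ≥ r), X ~ Binomial(n, p).

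| Rule | Unacceptable rate | Acceptable rate | Plan states |
|---|---|---|---|
| Acceptance 80/114 | 14.4% | 53.0% | 5% / 96% |
| Completion 68/80 | 11.6% | 57.6% | 5% / 96% |
| Acceptance 100/140 | 6.4% | 39.5% | approx. 5% / 96% |
| Completion 85/100 | 8.5% | 56.8% | approx. 5% / 96% |

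Read jointly, with the two components independent:
- Table 1 rule: 0.144 × 0.116 = 1.7% and 0.530 × 0.576 = 30.5%.
- Power-text rule: 0.064 × 0.085 = 0.5% and 0.395 × 0.568 = 22.5%.

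Reading the rules as strictly more than r, or using a normal approximation, does not rescue the pair. For example, strictly more than 100/140 gives 4.4% and 32.6%. A 96% pass probability would need a true acceptance of about 77% and a true completion of about 90%. So no reading tried gives 5% together with 96%.

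**Step 2: the 70% yardstick at a fixed end of enrolment.** With m enrolled, the yardstick is met if the m-th consent comes by approach number m/0.70, rounded down.
- m = 90: 90/0.70 = 128.6, so 90 by the 128th. At 65%: 12.1%. At 70%: 51.3%.
- m = 130: 130/0.70 = 185.7, so 130 by the 185th. At 65%: 7.6%. At 70%: 50.4%.

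**Step 3: the same yardstick if closing may follow the running rate.** An exact recursion over (approached, enrolled) counts a pass at the first look with 90 to 130 enrolled and enrolled/approached at least 0.70. It counts a fail if 130 is reached without one. At a true 65%:
- a look after every woman: 19.3%;
- a look every 7 approached: 16.6%;
- a look every 14 approached: 15.6%.

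The spacings of 7 and 14 assume about 180 women approached over 12 or 6 months with a look every two weeks: 180/26 ≈ 7 and 180/13 ≈ 14. At a true 70%, looking after every woman raises the pass probability to 68.1%.

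**Step 4: joint error under free closing.** Largest acceptance figure times the larger completion figure: 0.193 × 0.116 = 2.2%.

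**The case against.** A reader might infer that the team reviews the acceptance rate every two weeks and may stop when it passes 70%, and that this is what breaks the 5%. The documents do not support that, for four reasons.

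- The regular meetings cover accrual and enrolment problems. Nothing says that the 70% criterion is evaluated there or that enrolment can be closed on it.
- The 5% belongs to the fixed-denominator rules. Those count only the first 114 or the first 140 women approached, so carrying on longer cannot inflate them, and closing early can only make 100 by the 140th harder to reach.
- The 5% already fails at a single look (14.4% or 6.4%), with no stopping freedom involved.
- On the joint wording of the Power text, even free closing leaves the combined error at about 2.2%, below 5%.

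The arm sizes of 65 and 65 and the site split also point to 130 as the working target, and 6-12 months reads as an allowance for slow accrual. Nor is it right to say without qualification that free closing doubles the error. That holds against a fixed 130 (7.6%); against a fixed 90 (12.1%) the increase is about 4 to 7 percentage points.

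All of this stands. It removes any suggestion of intended stopping on the rate. It does not say which rule governs, give the yardstick a denominator, supply a closing rule for the 90-130 range, or reproduce the 5% and 96%.

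**Conclusion.** The point holds as a problem of unreconciled sizes and rules, with stated operating characteristics that the design does not deliver. On Table 1's per-component reading, acceptance passes with probability 14.4% rather than 5% at the unacceptable rate under 80/114, and 6.4% under 100/140. At the acceptable rate it passes with probability 53.0% or 39.5%, not 96%. The shortfall in power is the larger error: a trial with acceptance exactly at the level the plan wants has roughly an even chance, or less, of being called feasible on this component.

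The dependence on closing time is an additional and conditional weakness. It arises only if the denominator-free 70% yardstick decides the matter at the end of enrolment. The false-pass rate at 65% is then 7.6% to 12.1% for a fixed end at 130 or 90, and about 16-19% if closing may follow the running rate. These figures assume independent acceptance at a constant rate and, for the upper range, looks between every woman and every 14 approached. The plan permits such closing by silence; it does not provide for it.

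**What to change.** In sections 3.2.3 and 5.1:

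1. State one enrolment target with a calendar limit in place of the 90-130 range.
2. Judge acceptance once, at one pre-fixed number approached, whatever the final enrolment; for example, 100 or more of the first 140, as the Power text already has it.
3. State that enrolment does not end on the observed acceptance rate.
4. Drop the other acceptance rules or align them with the chosen one, including the 70% yardstick and the 80-by-114 row, and align the completion rule with the same sample.
5. Replace the 5% and 96% in Table 1 and the Power text with exact binomial values for the chosen rule, and say whether they apply per component or jointly. For 100/140 the acceptance values are about 6.4% and 39.5%; for 85/100 the completion values are 8.5% and 56.8%.

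The choice of bar matters. A flat 70% at the same look, 98 of 140, passes 12.4% of the time at a true 65%, so fixing the look alone does not bring the error to 5%.

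The cost is a few sentences and a corrected table, with no extra patients. The stated operating characteristics become less favourable, and the team gives up the freedom to close early on a favourable rate.

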3.3 Study Sites

Recruitment of participants and all human subjects' interactions will take place at Rutgers, Cancer Institute of New Jersey for Phase 1 and at Rutgers CINJ, Memorial Sloan Kettering Cancer Center (MSKCC) and Massachusetts General Hospital (MGH) for Phase 2. [name] involvement in the project will be as a consultant during Phase 1 of the study where she will provide input into the development of the decision aid. MGH and MSKCC will not begin participant recruitment until year 2.

3.4 Duration of the Study

In Phase 1, Step 1: Participants will be asked to attend one 60 minute interview.

In Phase 1, Step 3: Participants from step 1 will be asked to attend one 90 minute interview to provide feedback on module and to complete a prototype evaluation.

In Phase 2: CPM-DA FEASIBILITY TRIAL participants will provide feedback over the course of 6 months.

3.5 Study Enrollment Procedures

A copy of the institution's IRB-approved informed consent document and written justification for any changes made to the informed consent for this protocol must be on file at the Rutgers Cancer Institute of New Jersey's Office of Human Research Services (OHSR) before any participating institution may enter patients. Consent forms proposed for use at a participating

institution must be reviewed and approved by the OHRS Regulatory Affairs Manager and all documents must be received (i.e., IRB approved documentation, IRB approved consent form, etc.).

Participants who complete the online surveys will be asked to acknowledge online consent in the survey program before beginning the baseline survey through Qualtrics.

To register eligible patients on this study, each site will work with the study team and the Rutgers Cancer Institute of New Jersey's Program Coordinator for completion of the signed and dated eligibility checklist, completed signature page of the consent form and additional source documents if requested. Once eligibility has been verified, a unique patient study number will be issued. This is the point that the patient is considered on study. Patients must not start any study designated items prior to registration aside from consent and following the consent procedure the completion of baseline survey. Patients must not start any other study designated items prior to registration.

4. Study Variables

4.1. Measures

A preliminary overview of the study measures is shown in Table 1. We will utilize concise, psychometrically valid measures used in our prior research or that of other research groups.

	Baseline	FU 1 (Around post- op appointment 2-4 weeks post-surgery)	FU 2 (6 months)
Background Variables			
- Sociodemographic characteristics	✓	---	---
- Knowledge of CPM	✓	✓	✓
Psychosocial Factors	✓	✓	✓
- Risk Perception	✓	✓	✓
- Reasons for CPM	✓	✓	✓
- Self-Efficacy	✓	✓	✓
- Social influence	✓	---	---
- Importance of Input	✓	✓	✓
Decision Factors	✓	✓	✓
- Satisfaction with/Completeness of Preparation	✓	✓	✓
- Decision Conflict	✓	✓	✓
- Interest/Intention	✓	✓	✓
Process Evaluation of DA (DA arm only)	---	✓	---

4.1.1 Baseline survey (15-20 m).

4.1.2. Demographics. Basic demographics and technology skills will be assessed.

4.1.3. Knowledge. 11-items evaluate CPM knowledge ([name], personal comm., September, 2013).

4.1.4. Psychosocial factors. 1) *Risk perception*- 3 items estimate risk for breast cancer in the other breast and how much CPM reduces risk (Rosenberg et al., 2013); 2) *Reasons for CPM*-11 reasons (Rosenberg et al., 2013); will be assessed; 3) *Self-efficacy*-3 items assess confidence in managing worry about cancer recurrence, complying with surveillance, and worry about surveillance. 4) *Social influence*- Item asks how much doctors talked about reasons to have/not have CPM; 5) *Importance of input*-Items ask how important input from surgeon, nurse, family/friends, internet, media is in the decision (Rosenberg et al., 2013).

4.1.5. Decision factors: *Satisfaction with/completeness of preparation.* The Satisfaction with the Decision-making Process Survey (Barry et al., 1997) assesses satisfaction with a number of factors including the amount of information, how information was presented, and how prepared they are to make a decision.

4.1.6. Decisional conflict. The Decisional Conflict Scale (Anderson, 2009) is a widely used scale. CPM interest/intention. Made a CPM decision; if not, rate CPM intentions.

4.2. Follow-up Measures

4.2.1. Follow-up surveys (20m). All baseline measures except demographics will be given.

4.2.2. Process Evaluation: 1) *DA Evaluation* (DA arm only). Ratings include: extent that they used the DA, comprehensiveness of information, whether it presented material in a balanced manner, whether it influenced the decision, whether it was helpful in making the decision, whether it was helpful in understanding pros and cons, and whether they used the information in a discussion with the surgeon. Items are based on Brug (Brug et al., 2005) and previous research ([name] et al., 2010; [name] et al., 2005) 2) *DA implementation evaluation.* We will assess: a) log ins and time in DA; b) time spent in each module; c) number of pages printed out/sent to mobile device; d) ease of accessing and navigating the web-based application at home or at the center; 3) *User Interface Satisfaction* (Lund, 2001) assesses usefulness, ease of use, ease of learning and satisfaction with online tools. Feedback will be collected at the time of the first follow-up survey, but we may also contact participants by phone for a short debriefing on their experience with the site.

4.2.3 Risk and procedures for handling adverse events.

This study involves research presenting little risk. There are no physical risks or side effects associated with participation. If the participant is experiencing any psychological distress, as reported by the patient to the study staff, the study project coordinator will inform [name]. [name] will then determine if contacting the participant is necessary and/or helpful to evaluate distress levels and refer if further assistance is needed or requested. There are psychosocial resources available for patients. These procedures have been implemented successfully with our previous psychological intervention trials.

4.2.3.1. Adverse Events: In the proposed study, we define adverse events as psychological distress by the method outlined above, the following procedure for handling this event are: 1) the site PI will inform the IRB about the event; 2) the PI, [name], will be informed and this event will be reported to the Rutgers Cancer Institute of New Jersey IRB.

As with all research that collects protected health information, there is a risk that participants' confidentiality could be compromised during the study.

4.3 Data and Safety Monitoring

Data Safety and Monitoring Advisory Board. Monitoring of this study will occur in accordance with the Rutgers Cancer Institute of New Jersey's NCI approved Data and Safety Monitoring Plan (DSMP).

In order to insure the safety of participants and the integrity of the study, a data and safety monitoring plan will be put into effect. As part of this plan, all adverse events will be reported through Rutgers Cancer Institute of New Jersey for processing as per established policy.

The project coordinator, under the direct supervision of the principal investigator, will be responsible for reporting any adverse events that are documented on the safety/adverse events form or are reported by the study interventionist.

We will identify a group of Rutgers Cancer Institute of New Jersey Cancer Prevention and Control Program investigators who will serve as our Data Safety and Monitoring Advisory Board. This team will consist of 2 investigators from Rutgers Cancer Institute of New Jersey who will review our risk procedures, adverse event reporting procedures and quality assurance procedures in Year 2. They will review any serious adverse events reported and adherence to our eligibility rules.

